16.1.3 Exploratory Endpoint

The exploratory endpoint is to quantify the abscopal effect experienced by participants after their injections. Participants' charts will be reviewed to assess the number of nonmelanoma skin cancers before and after the intervention. The frequency of NMSCs before the intervention will include the 12 month and 24 month period before the first injection visit (or Visit 1). The frequency of NMSCs after the intervention will include the 12 months after the last injection visit (or Visit 4) and then 24 months after the last injection (or Visit 4) if available.

16.2 Statistical Analysis

Any patient who was treated with at least 1 dose of talimogene laherparepvec therapy will be included in safety and efficacy analysis. Descriptive statistics (mean, median, standard deviation, 25th percentile, 75th percentile, and range) will be presented for continuous variables, such as age. Frequency counts will be presented for categorical variables such as sex and race.

16.2.1 Overall Response Rate (ORR)

The analysis of ORR will use a Simon two-stage optimum design to test that the proportion with ORR is \geq 80% (alternative hypothesis) versus ORR \leq 50% (null hypothesis). In the first stage, 7 patients will be recruited. If \leq 4 have ORR the trial will be terminated. If 5 or more have ORR, accrual will continue to the second stage. In the second stage, an additional 13 patients will be recruited. At the end of the second stage, if \geq 14 patients have ORR then TVEC will be considered promising for further study. This design yields 80% statistical power with a one-sided alpha level of 0.05.

16.2.2 Safety and Adverse effects of talimogene laherparepvec in cSCC

Summary statistics (counts, percentage, mean, standard deviation, etc.) will be presented for the safety and adverse endpoint as appropriate. Grading of adverse effects will be done as per CTCAE 4.03 grading of the National Cancer Institute.

16.2.3 Duration of overall response (DOR) of TILs.

Once a PR or CR has been established, the analysis will consist of Kaplan-Meier estimates. The analysis will also include a median and a 95% 1-sided exact confidence interval.

16.2.4 Durable Response Rate of TILs.

Once a PR or CR has been established, the analysis will consist of Kaplan-Meier estimates. We will consider durable response when continuously PR or CR is sustained for at least 6 months. The analysis will also include a median and a 95% 1-sided exact confidence interval.

16.2.5 Time to progression (TTP) of TILs.

The analysis of time to response will consist of Kaplan-Meier estimates. The median time and 95% confidence interval will be presented.

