9.4.1.1 Tumor Response

Complete Response (CR): Complete disappearance of all TILs (whether measurable or not, and no new lesions at the site of injection) confirmed by an assessment 8 weeks after the end of the injections (Visit 6).

Partial Response (PR): Decrease in tumor burden $\ge 30\%$ relative to baseline confirmed by an assessment 8 weeks after the end of the injections (Visit 6).

Duration of Overall Response (DOR): DOR is when the time measurement criteria are met for CR or PR (whichever status is recorded first) until the first date that recurrence or progressive disease (PD) is objectively documented, taking as reference for PD the smallest measurements recorded since the treatment started. If no recurrence or PD is documented after PR or CR is observed the time measurement will be performed at Visit 6 for PR and Visit 8 for CR.

Durable Response Rate (DRR): Measured from the time measurement criteria are met for CR or PR (whichever status is recorded first) with the response lasting continuously for > than or equal to 6 months. For PD, the reference will be the
smallest measurements recorded since the treatment started.

Time to progression (TTP): This will be measured from the time treatment is initiated until the first date that recurrence or progressive disease (PD) is objectively documented, taking as reference for PD the smallest measurements recorded since the treatment started.

Progressive Disease (PD): Progression is defined as >20% increase of at least 5 mm in the sum of the longest diameters of the target lesions or increase in tumor burden $\ge 20\%$ relative to nadir (minimum recorded tumor burden) or the appearance of one or more new lesions confirmed by an assessment 8 weeks after the end of the injections (Visit 6).

• **Rapid PD (RPD):** Is defined as an increase of >50% in tumor burden for lesions >2 cm in diameter or 100% tumor burden increase for lesion ≤2cm between visits.

Stable Disease (SD): Not meeting criteria for CR or PR, in absence of PD (Decrease of tumor size <30% to increase in size <20% of less than 5 mm in the sum of the longest diameters of the target lesions).

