16.1.2 Secondary Endpoints

 To assess the safety and adverse effect profile of talimogene laherparepvec in low risk cSCC. Adverse events to be assessed according to National Cancer Institute Common Terminology. This will be determined by incidence of all adverse events (AEs), grade ≥ 3 AEs, safety adverse events (SAEs), and events requiring the discontinuation of study drug, local effects on the tumor (ie, pain, inflammation and ulceration), and any clinically significant laboratory values.

- 2. Time to response in cSCC TILS. Time to response is the time from first visit until objective tumor response (CR or PR) is identified
- 3. Duration of overall response (DOR) of TILs. This will be measured from the time measurement criteria are met for CR or PR (whichever status is recorded first) until the first date that recurrence or progressive disease (PD) is objectively documented, taking as reference for PD the smallest measurements recorded since the treatment started. If no recurrence or PD is documented after PR or CR is observed the time measurement will be performed at Visit 8.
- 4. Durable response rate of TILs. The duration of overall response is ORR lasting continuously for > than or equal to 6 months.
- 5. Time to progression (TTP) of TILs. This will be measured from the time treatment is initiated until the first date that recurrence or progressive disease (PD) is objectively documented, taking as reference for PD the smallest measurements recorded since the treatment started.
- 6. Overall response rate (CR+PR) of TILs assessed by imaging technique (high frequency ultrasound) and correlate it with clinical overall response rate.
- 7. Overall clinical response rate (CR+PR) of individual TILs injected with talimogene laherparepvec (not as overall subject response). Overall response rate is defined as the proportion of injected lesions which achieved complete and partial response.

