16.2.6 Time to response in TILs

The analysis of time to response will consist of Kaplan-Meier estimates. The time to response data will be censored on those who do not respond at their last follow-up. The median time and 95% confidence interval will be presented.

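### The Kaplan-Meier median duration of response is given a one-sided exact 95% interval, which censored data do not generally allow; the bound is not named, and the same sentence puts a median on the durable response rate

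*Combined protocol and SAP*

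**What the plan says.** - **DOR, Section 16.2.3.** The estimator is stated: "Once a PR or CR has been established, the analysis will consist of Kaplan-Meier estimates". The interval follows: "The analysis will also include a median and a 95% 1-sided exact confidence interval". Neither the bound (lower or upper) nor the exact method is named, here or elsewhere.
- **Durable response rate, Section 16.2.4.** The same two sentences appear, with this definition between them: "We will consider durable response when continuously PR or CR is sustained for at least 6 months".
- **Time to progression and time to response, Sections 16.2.5 and 16.2.6.** Both have Kaplan-Meier estimates and the sentence "The median time and 95% confidence interval will be presented". Sidedness and method are not stated, and the interval is not called exact.
- **Cut-off for responders without an event.** Section 16.1.2 says: "If no recurrence or PD is documented after PR or CR is observed the time measurement will be performed at Visit 8". Section 9.4.1.1 says instead that "the time measurement will be performed at Visit 6 for PR and Visit 8 for CR".
- **Primary test, Section 16.2.1.** "This design yields 80% statistical power with a one-sided alpha level of 0.05". This is the only other one-sided statement in the analysis plan.

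**The concern.** Exact distribution-free limits for a median are order statistics: the limit is the k-th smallest duration, with k read from a binomial distribution with probability one half. That needs the k-th smallest duration to be known, which right-censoring can prevent. The usual limits for a Kaplan-Meier median are large-sample approximations. The phrase in 16.2.3 therefore describes an interval that does not in general belong to the estimator it is attached to.

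Two things follow. First, whoever runs the analysis must choose a bound and a method after seeing the data. Second, the label 95% would mean a different error per limit for DOR than for the two neighbouring time-to-event endpoints, if those are two-sided. In 16.2.4 the mismatch is of another kind: a rate has no median, so the planned summary does not answer the stated endpoint.

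**Working it through.** **1. The plan's own figures.** The documents give no number for the DOR interval. The nearest stated figures are the primary design: 7 then 13 patients, continue at 5 or more responders, success at 14 or more of 20. The probability of success is the sum over x = 5 to 7 of P(Bin(7, p) = x) × P(Bin(13, p) ≥ 14 − x). It is 0.0417 at p = 0.5 and 0.812 at p = 0.8, so the stated 0.05 and 80% reproduce. Below I assume 16 responders (80% of 20) and, as a second case, 14 (the success threshold).

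**2. Follow-up after response (nominal visits, Table 1).** Weeks to Visit 8:

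| First recorded at | Sum | Weeks |
|---|---|---|
| Visit 2 | 2+2+4+4+6+14 | 32 |
| Visit 4 | 4+4+6+14 | 28 |
| Visit 5 | 4+6+14 | 24 |
| Visit 6 | 6+14 | 20 |

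Under the Visit 6 cut-off for PR in 9.4.1.1, a PR would have between 0 weeks (first recorded at Visit 6) and 2+2+4+4 = 12 weeks (Visit 2).

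**3. Exact limits without censoring.** The lower limit is the k-th ordered duration, with k the largest value for which P(Bin(n, 0.5) ≤ k − 1) does not exceed the tail allowed.

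| n | One-sided 95% | Two-sided 95% |
|---|---|---|
| 16 | 5th; tail 2517/65536 = 0.038; coverage 96.2% | 4th to 13th; tail 697/65536 = 0.011; coverage 97.9% |
| 14 | 4th; tail 470/16384 = 0.029; coverage 97.1% | 3rd to 12th; tail 106/16384 = 0.0065; coverage 98.7% |

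**4. When the lower limit stays exact under censoring.** The k-th duration must precede the first censoring time. Assume exponential durations with true median m weeks, no earlier loss, and first censoring at 20 weeks. The chance that one duration ends before then is p = 1 − 2^(−20/m): 0.603, 0.413 and 0.234 for m = 15, 26 and 52. For n = 16, P(Bin(16, p) ≥ 5) is 0.995, 0.86 and 0.31. For n = 14, P(Bin(14, p) ≥ 4) is 0.996, 0.895 and 0.42. Availability thus depends on the data and falls as responses last longer. Early loss, or the Visit 6 cut-off for PR, would lower it.

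**5. Kaplan-Meier bounds.** Simulation, 4,000 runs per setting: 14 or 16 responders, exponential durations, true median 15 or 26 weeks, censoring uniform on 20 to 32 weeks, with or without random loss. Censoring was 30–59%. One-sided lower bounds with nominal 95% coverage covered:
- 91.0–96.7% on the plain scale;
- 95.5–97.3% on the log-log scale.

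These are approximate bounds, and the choice of scale matters. A one-sided upper bound was not reached in 38–53% of runs at a 15-week median and 87–88% at 26 weeks. The median itself was not reached in 2–8% and 34–43%.

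**6. Level per limit.** One-sided 95% uses z = 1.645 (5% in the tail). Two-sided 95% uses z = 1.960 (2.5% per tail). The one-sided bound is one limit of a two-sided 90% interval.

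**The case against.** The strongest defence is that a lower bound is the informative side for duration in a single-arm phase 2 trial, and that one-sided 95% matches the one-sided 0.05 of the primary test. Planned censoring is also late, so the few early durations that an exact lower limit needs may well all be observed. Step 4 supports this for shorter durations.

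Much of that stands. One-sidedness is not wrong in itself, and a reader who infers from the censoring that an exact limit cannot be computed at all would be going too far. But the plan does not say that the lower bound is meant, does not link it to the primary alpha, plans no test of DOR, and gives no rule for when the exact limit fails.

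Two other inferences also fail. An interval open on one side is unbounded, so it does not look tighter than its neighbours, which concern different quantities. And the difference in level from 16.2.5 and 16.2.6 rests on reading those intervals as two-sided, which is convention and not stated.

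**Conclusion.** The point holds as a mismatch between the stated interval and its estimator, together with an unnamed bound and method. It is minor. DOR and the durable response rate are two of eight secondary endpoints, and the documents do not call either one key. No sample size, decision rule or primary result changes, so a reader should not infer any doubt about the primary design.

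The size is a shift of one order statistic in the lower limit in the uncensored illustration, and 5% against 2.5% error per limit. The illustrations rest on assumed numbers of responders, exponential durations and nominal visit dates. The mismatch in 16.2.4 needs none of these: a proportion has no median.

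The two cut-off rules for DOR contradict each other and determine how much censoring there is, so no interval method can be fully specified until they agree.

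**What to change.** - **16.2.3:** replace the phrase with a two-sided 95% Brookmeyer-Crowley interval (log-log transform) for the Kaplan-Meier median, with the median or a limit reported as not reached where that applies.
- **16.2.5 and 16.2.6:** name the same method and state that the intervals are two-sided.
- **16.2.4:** drop the median. Report the proportion with a response of at least 6 months with a two-sided 95% interval. An exact binomial interval suits if every responder's 6-month status is known; otherwise use the Kaplan-Meier proportion at 6 months. Show numbers at risk, because responses first recorded at Visit 5 or 6 have only about 24 or 20 weeks to Visit 8, short of 26. The 6-month estimate rests mainly on responses recorded by Visit 4 and may itself not be estimable.
- **9.4.1.1 and 16.1.2:** reconcile the DOR cut-off for responders without an event.

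The cost is wording, with no added patients, visits or data. The lower limit may be slightly lower: the 4th instead of the 5th ordered duration with 16 uncensored responders, or the 3rd instead of the 4th with 14. The change should be made before the response durations are analysed.

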16. STATISTICAL CONSIDERATIONS

16.1 Analysis Endpoints

16.1.1 Primary Endpoint

The primary end point is to evaluate the overall response rate (ORR) defined as proportion of subjects who achieved CR and PR in the cSCC TILs. Clinical assessments will be done using a ruler or calipers. Digital photograph of the lesion(s) will be recorded each visit. Through clinical evaluation, CR will be defined as the complete disappearance of all TILs and PR will be defined as at least a 30% decrease in the sum of the diameters of TILs, taking as reference the baseline sum diameters. Progression is defined as >20% increase of at least 5 mm in the sum of the longest diameter recorded or increase in tumor burden \ge 20% relative to nadir (minimum recorded tumor burden) or the appearance of recurrent lesions confirmed by an assessment 8 weeks after the end of the injections (Visit 6). Stable disease (SD) is defined as decrease in tumor size <30% or an increase in size <20%.

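### Section 16.2.4 gives the durable response rate a responder-only duration analysis that does not output the rate, and the sections disagree (Visit 6 or Visit 8) on where DOR ends for an ongoing PR

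*Combined protocol and SAP*

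**What the plan says.** **Endpoint.** Under durable response rate, 16.1.2 item 4 (and 3.2 item 4) says: "The duration of overall response is ORR lasting continuously for > than or equal to 6 months". Section 16.1.1 defines ORR as a rate, "defined as proportion of subjects who achieved CR and PR in the cSCC TILs". Section 9.4.1.1 sets the DRR clock: "Measured from the time measurement criteria are met for CR or PR (whichever status is recorded first) with the response lasting continuously", again for six months or more.

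**Population.** Section 16.2: "Any patient who was treated with at least 1 dose of talimogene laherparepvec therapy will be included in safety and efficacy analysis".

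**Analysis.** Sections 16.2.3 (DOR) and 16.2.4 (DRR) share two sentences: "Once a PR or CR has been established, the analysis will consist of Kaplan-Meier estimates" and "The analysis will also include a median and a 95% 1-sided exact confidence interval". The only addition in 16.2.4 is the six-month threshold, "We will consider durable response when continuously PR or CR is sustained for at least 6 months".

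**End of measurement for DOR.** For a response without recurrence or PD, 9.4.1.1 says "the time measurement will be performed at Visit 6 for PR and Visit 8 for CR". Section 3.2 item 3 and 16.1.2 item 3 name Visit 8 for both PR and CR.

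**The concern.** The endpoint is a proportion of subjects. The prescribed analysis gives a curve that starts only once a subject has responded, and a median, which is a time. An analyst following 16.2.4 literally would produce a second copy of the DOR analysis and no durable response rate. The figure closest to hand would be the six-month point on the responder-only curve, and quoting that as the DRR leaves the non-responders out of the denominator.

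The second problem is a direct contradiction about when the duration of an ongoing PR stops being counted. Two analysts working from different sections would get different DOR values from the same data. Because 16.2.4 uses the same Kaplan-Meier durations, the choice also decides whether an ongoing PR can ever count as durable.

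**Working it through.** **The plan's own figure.** No sample size, power or target is stated for DRR or DOR. The only design figure is the Simon rule for ORR in 16.2.1: 7 then 13 patients, continue with at least 5 responders, promising with at least 14 of 20. The exact probability of success is the sum over x = 5 to 7 of P(Bin(7, p) = x) × P(Bin(13, p) ≥ 14 − x). This gives 0.0417 at p = 0.50 and 0.812 at p = 0.80, in line with the stated 0.05 and 80%. Nothing below depends on it.

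**What 16.2.4 outputs, against the endpoint.** Let R be response and D its duration.

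- The 16.2.4 curve estimates S(t) = P(D > t given R). The median is the time at which S falls to 0.5.
- The endpoint, with all treated patients as denominator, is P(R and D ≥ 6 months) = ORR × S(6 months).
- With complete follow-up, the responder-only figure divided by the all-treated figure is therefore 1/ORR. This is 1/0.50 = 2.00 at the plan's null rate, 20/14 = 1.43 at its success boundary and 1/0.80 = 1.25 at its alternative.

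Illustrative counts, assumed because the documents give none (20 treated, complete follow-up):

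| Responders | Durable | Among responders | All treated | Exact one-sided 95% lower limit, all treated |
|---|---|---|---|---|
| 14 | 10 | 71% | 50% | 30.2% |
| 16 | 8 | 50% | 40% | 21.7% |
| 10 | 8 | 80% | 40% | 21.7% |

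**Time available to observe six months.** The visit intervals in 2.4 and 9.3 give nominal days from Visit 1: V2 21, V3 35, V4 49, V5 77, V6 105, V7 147, V8 245. Visit 8 is the last visit with measurements. Windows in 9.7 are ±3 days for V1–V4, ±7 for V5–V6, ±10 for V7 and ±21 for V8. The maximum adds every window after the first-response visit.

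| Response first recorded at | Days to V6, nominal | Days to V8, nominal | Days to V8, maximum |
|---|---|---|---|
| V2 | 84 | 224 | 275 |
| V3 | 70 | 210 | 258 |
| V4 | 56 | 196 | 241 |
| V5 | 28 | 168 | 206 |
| V6 | 0 | 140 | 171 |

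The V6 maximum, for example, is 140 + 10 + 21 = 171. The documents do not convert six months to days, so I assume a range:

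- At 181–184 days (six calendar months), first responses at V2–V4 can qualify on the nominal schedule, V5 only with late visits, and V6 not at all.
- At 168 days (24 weeks), V5 qualifies nominally and V6 only at the edge of the windows.

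A proportion based on documented six-month responses is therefore a lower bound.

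**The DOR contradiction.** For an ongoing PR, the difference between stopping at Visit 8 and at Visit 6 is 245 − 105 = 140 days. Under the Visit 6 rule the longest possible ongoing PR is 84 days nominally (first recorded at V2), or 84 + 3 + 3 + 7 + 7 = 104 with every window stretched. Both fall short of six months on either day count. Yet 16.2.4 expressly counts a sustained PR as durable.

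**The case against.** The best defence of 16.2.4 is that the rate can be recovered. The section states the six-month threshold, so a reader can take the Kaplan-Meier curve at that point. Multiplying by ORR, which is reported anyway, gives an all-treated rate. The word exact suggests a binomial interval, and 16.2 supplies the denominator. This is fair as far as it goes: the fault is an unstated readout and denominator, and the data needed are collected. But the section names neither the six-month estimate nor the multiplication, and the summary it does name is a median.

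A proportion based only on documented durable responses also has a bias. It counts an ongoing response with short follow-up as not durable, whereas Kaplan-Meier properly censors it. That objection stands, and it is why the documented proportion should not be shown alone.

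On DOR, the 9.4.1.1 wording could mean only when an assessment is made. Its place in the DOR definition, parallel to the Visit 8 sentence elsewhere, makes the end of measurement the natural reading.

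Three stronger inferences are tempting but not supported:

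- *That the whole gap between a responder-only Kaplan-Meier figure and the documented all-treated proportion is a denominator error.* With censoring, part of the gap comes from how ongoing responses are counted. The documents give no time-to-response data from which to size that part.
- *That Table 7's six months of follow-up for a lesion CR cannot fit the schedule.* Table 7 gives no start for that period. Counted from the last injection, Visit 4 to Visit 8 is 196 days.
- *That follow-up stops at Visit 8 and so conflicts with the Visit 9 call.* Section 9.8 keeps subjects on study until all planned follow-up visits are completed, and the schedule in Section 26 includes the telephone contact.

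**Conclusion.** The point holds in two parts, and both should be fixed.

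(a) As written, 16.2.4 does not output the durable response rate. If the responder-only figure is taken for it, the all-treated rate is overstated by a factor of 1/ORR: 1.25 to 2.00 across the plan's hypothesised ORR range, and 1.43 at 14 of 20. That size assumes complete follow-up; with censoring the ratio differs.

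(b) Section 9.4.1.1 contradicts 3.2 and 16.1.2 on the end of DOR for an ongoing PR, by 140 nominal days. Applied to the 16.2.4 durations, the Visit 6 rule would exclude every ongoing PR from being durable.

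The text of both parts is unambiguous; the counts in the examples are assumptions. A reader might infer that the trial's main conclusion is at risk. It is not: these endpoints are secondary and carry no test.

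**What to change.** 1. **16.2.4.** Keep the six-month definition and delete the median. Report DRR as the proportion of all treated subjects with CR or PR documented continuously for at least six months, with the one-sided 95% exact interval applied to that proportion. Label it a lower bound, because first responses at Visit 5 or Visit 6 have only 168 or 140 nominal days to Visit 8.
2. **Beside it,** report the six-month Kaplan-Meier probability among responders, labelled as such and with the number still at risk. Add the all-treated version, ORR times that probability, which is the same as giving non-responders zero duration.
3. **9.4.1.1.** Reconcile it with 3.2 and 16.1.2 so that one end of measurement applies to PR and CR, with ongoing responses censored there. Visit 8 is the natural choice: it is the last measured visit, two of the three definitions already use it, and Table 7 follows a continuing lesion PR to it.

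The cost is wording in 9.4.1.1 and 16.2.4 (and the censoring statement in 16.2.3), plus one extra line of analysis. Sample size, visits and the primary test do not change. The downside is a less favourable headline durability figure.
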